- D. Once eligible to receive treatment, Omegaven® will be given at any time the infant requires PN and has a conjugated bilirubin > than 2 mg/dl.
- E. Discontinuation of treatment would also include such factors as development of contraindications for further use or request by family / guardian to be removed from protocol.
- F. In the event that a patient is unable to achieve adequate calories parenterally and is unable to tolerate enteral feeds, it may be necessary to evaluate whether or not the patient should continue the treatment with Omegaven® as monotherapy or resume therapy with conventional fat emulsions or a trial of SMOFLIPIDs for the qualified infants so that additional parenteral fat calories can be given. The attending neonatologist, in conjunction with the Principal Investigator, will determine if the patient should be removed from the Omegaven treatment protocol.

Sample Size

- The number of patients included in the Omegaven® group will be based on a compassionate use protocol and not on treatment power considerations.

4. Patient Withdrawal/ Termination

The patient will be withdrawn from the treatment after review by the Principal Investigator for reasons which may include:

- Allergic reaction or anaphylaxis due to use of Omegaven®
- Active bleeding
- Hypotension during infusion
- Hyperglycemia during infusion
- Triglycerides >600 mg/dL

- Toxicities considered unacceptable by the Principal Investigator which require adverse event assessment and reporting, are severe in nature and are related to Omegaven®. These include anaphylactic or allergic reactions, death, blood stream infections, respiratory distress, hemodynamic instability, re-hospitalization for treatment of blood stream infection, dehydration, electrolyte abnormalities, catheter malfunctions, bowel obstructions and urinary tract infection.
- Guardian requests to discontinue treatment and/or observation for any reason
- Decision by the Principal Investigator that termination is in the patient's best medical interest

In the event that the patient is withdrawn from participation, the Principal Investigator will document the date of withdrawal, the reason for withdrawal, and the results of all measurements of interest made up to date of withdrawal.

5. Omegaven Supply and Administration:

Omega-3 Fat Emulsion (Omegaven®) Supply:

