Bottles containing 50mL or 100 mL of 10% Omegaven® will be purchased from Pharmacy International of Hamburg, Germany or directly from the manufacturer. Omegaven® is manufactured by Fresenius Kabi AG, Bad Homburg v.d.h, Germany. Omegaven® is formulated as an emulsion from fish oils. We are applying for FDA permission for patient insurance company billing.

All treatment materials will be stored securely until the time of administration. The bottles will be stored at room temperature below 30°C (do not freeze). Damaged or suspect drug will be returned unused to Fresenius-Kabi. Containers should be shaken before use. All supplies for the treatment will be accompanied by accountability and shipping documents and will be maintained by the Research Pharmacy at TGH. Information recorded on these accountability and shipping documents will include relevant dates, batch numbers, quantities received or dispensed, to whom dispensed, returned drug and drug lost or damaged. At the end of the treatment plan, all used and unused Omegaven® will be accounted for. If expired, the remaining drug supplies will be destroyed.

Omegaven® Administration

Therapy with Omegaven® will be initiated at the goal dose of 1 g /kg/day. The default is over 24 hours but shorter intervals may be considered if a program of TPN cycling is later recommended. Omegaven™® will be infused intravenously through either a central or peripheral catheter alone or in conjunction with parenteral nutrition. The emulsion is isotonic and is compatible with parenteral nutrition solutions and may be co-infused via y-site. Omegaven® will be infused separately from all other parenteral medications. The same standards of care provided to all patients receiving PN solution will be followed. Omegaven® will be dispensed per Tampa General Hospital policy and procedures for lipid emulsions.

Orders for Omegaven® will be written in the hospital EMR (EPIC) order form and must contain the following data elements:

- Total daily dose to administered in mL
- The hourly infusion (do not exceed maximum rate of 0.5 ml/kg/hr)
- Should not infuse without concurrent dextrose infusion

The patient will be monitored while receiving Omegaven® treatment to observe for signs of Omegaven™ toxicity. At the start of Omegaven® therapy, the patient will be monitored closely during and shortly after initial Omegaven® administration to observe for signs of allergic reaction and anaphylaxis. In the event

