the patient demonstrates signs or symptoms of allergic reaction, the Omegaven® may be temporarily discontinued and the Principal Investigator and attending neonatologist will be notified. Selected safety labs will be evaluated by attending staff and the Principal Investigator.

Dose Modification / Lipid Intolerance

If lipid intolerance develops, defined as serum triglyceride levels > 300 mg/dL, the following will be considered prior to reducing the dose:

- If the level was obtained while the patient was receiving a continuous 24 hours infusion of Omegaven®, the total dose should be infused over 20 hours, and a repeat serum triglyceride level obtained prior to resuming the infusion 4 hours later.
- Other sources of lipid intolerance will be considered and addressed (drugs, renal disease)

If the triglycerides continue to remain high despite the aforementioned interventions, a dosage reduction of 25% - 50% of the current dose will be considered.

Disruption of Therapy

In event that Omegaven® cannot be administered (i.e. loss of central venous catheter access, fluid restrictions, need to administer an incompatible medication/blood product), the infusion of Omegaven® may be interrupted and resumed when the conflicting situation is resolved.

Primary Safety Outcomes/Endpoints

1. Treatment safety: Lab values will be recorded/monitored as scheduled within Table 1. Consider coagulopathy panel if suspicious for bleeding disorder. Essential Fatty Acid (EFA) Deficiency has not been reported in the use of Omegaven at 1g/kg/d. If there is clinical suspicion or prolonged use of Omegaven at <1 g/kg/d, consider testing for EFA deficiency with triene:tetraene ratio.
2. Growth: At a minimum, monitoring of growth parameters while the patient is on Omegaven® will include weight three times per week, length once weekly, and head circumference once weekly.

Table 1: Monitoring Schedule for Omegaven® Therapy

Parameter	Baseline (pre-Omegaven) No more than 14 days prior to Omegaven® treatment.	Q week*	Q 4 weeks	Periodically as clinically indicated
Weight	X			
Fluid balance	X			
Vital Signs	X			
Catheter site/function	X			
Laboratory tests:				

Hepatic Function Panel (includes Total protein, Albumin, Total and Direct Bilirubin, AST, ALT, Alkaline Phosphate)	X	X		
Renal Function Panel (includes Ca, Phosphorus, Glucose, BUN, Creatinine, Albumin, Sodium, Potassium, Chloride, CO2)	X			x

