- The potential benefits of this therapy apply directly to the patient in question and to possible improvement in the treatment of future patients. If successful, the experimental treatment will provide a safe and effective means of avoiding liver failure requiring transplant or that may lead to death. Thus, the potential complications of surgery or fulminant hepatic failure may be avoided.
- PN associated liver disease is a life threatening condition. Available therapies (liver/small bowel transplant, intestinal lengthening, ursodiol, combination enteral/parenteral feedings) are often inadequate. Phytosterol containing IV fat emulsions containing large quantities of omega 6 fatty acids have been associated with PN associated liver disease. The safety profile of Omegaven® has been demonstrated to be acceptable for the diseases treated and should be considered as an option for patients requiring a form of IV fat emulsion.

Alternatives to Participation

The only other alternative is the FDA approved soybean emulsion. Non-FDA approved fat emulsion, SMOFLipids, is also available at TGH for certain population.

8. Unanticipated Problems

Adverse events (AEs) will be assessed and reported from the time of the first Omegaven® infusion until exit from the treatment plan in accordance with USF IRB and FDA reporting requirements. If the patient experiences any adverse events that are moderate or severe in nature and that may be related to Omegaven® will have their treatment temporarily halted until the adverse event has resolved. Dose modifications will occur as described above. If a dose reduction is made for adverse events later considered to be unrelated to Omegaven®, the Omegaven® dose will be increased back to the dose prescribed prior to the dose reduction. If the patient has an anaphylactic or allergic reactions will not continue Omegaven® treatment.

Adverse events will be detected by TGH NICU medical and nursing staff during provision of standard care services including the routine monitoring of vital signs and daily physical exam data. Adverse events identified by staff will be reported to the Principal Investigator and research team per USF IRB policy.

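### Adverse event recording ends at an undefined exit, so the protocol's own rules need not capture new events or deaths after a permanent withdrawal for toxicity

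*Protocol*

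**What the plan says.** Section 4 (Patient Withdrawal/ Termination) opens with "The patient will be withdrawn from the treatment after review by the Principal Investigator for reasons which may include" and lists eight reasons, among them severe toxicity related to Omegaven. Its data rule uses a different phrase: "In the event that the patient is withdrawn from participation, the Principal Investigator will document the date of withdrawal", together with the reason and "the results of all measurements of interest made up to date of withdrawal". Only one of the eight reasons names observation as something apart from treatment: "Guardian requests to discontinue treatment and/or observation for any reason".

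Section 3, Treatment Duration, item F covers an infant who may go back to another fat emulsion. The attending neonatologist and the Principal Investigator "will determine if the patient should be removed from the Omegaven treatment protocol".

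Section 8 (Unanticipated Problems) has adverse events assessed and reported "from the time of the first Omegaven® infusion until exit from the treatment plan", and adds that this follows the reporting requirements of the USF IRB and the FDA. It does not define the exit.

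In Section 5, monitoring is tied to time on the drug: "The patient will be monitored while receiving Omegaven® treatment to observe for signs of Omegaven™ toxicity", and "monitoring of growth parameters while the patient is on Omegaven® will include weight three times per week". Table 1 is headed as a schedule for Omegaven therapy. Section 9 plans to collect, among other things, the duration of PNALD, hospital stay and time to full enteral feeding for a before/after comparison. It states no cut-off.

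**The concern.** Stopping a drug and ending observation are different events, and a safety record depends on keeping them apart. An infant taken off Omegaven for a severe related toxicity is one whose later course matters most to a safety assessment. If the duty to record ends when the drug ends, the triggering event is captured. A new event a few days later, or a death, may not be.

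The only outcomes that the protocol labels as primary are safety outcomes. A record that follows its rules to the letter could therefore look more benign than the infants' actual course. A statistical analysis plan cannot repair this afterwards, because it cannot analyse what was not collected.

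**Working it through.** The protocol states no number of patients, withdrawal rate or adverse event rate, so there is nothing to compute. The check is to set the rules side by side and ask what each requires for one infant: permanently withdrawn for a related toxicity, still in hospital, guardian content with continued observation.

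1. **Section 4, data rule.** There are two readings.
   - If withdrawal from treatment and withdrawal from participation are the same event, required documentation ends on the day the drug is stopped for good.
   - If they differ, the rule does not apply to this infant, and Section 4 has no rule for an infant who is off the drug but still observed.
   - Neither reading creates a duty to record later events.

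2. **Section 8, reporting window.** There are again two readings.
   - If permanent withdrawal is the exit, the window closes that day.
   - If it is not, the window stays open, but no date or event closes it.
   - The first reading is the more natural one for a permanent withdrawal, because Section 4 passes straight from reasons for stopping treatment to a rule for ending participation, and item F speaks of removal from the treatment protocol.

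3. **Section 8, temporary halts.** Treatment is halted for moderate or severe, possibly related events until they resolve. This implies that the triggering event is followed while the drug is off. It says nothing about new events after a permanent stop.

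4. **Section 5 and Table 1.** Toxicity and growth monitoring run while the infant is on the drug, and the table schedules no assessment after treatment. These do not fill the gap.

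5. **Guardian request.** One reason in eight distinguishes observation from treatment. The authors saw that the two can be separated, but no procedure follows for an infant who stops one and continues the other.

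6. **Section 9.** Its outcomes can run past the last infusion and it has no cut-off, so it may be read as continuing after withdrawal. It does not name adverse events or deaths after withdrawal among its listed items.

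Result: on the natural reading, no rule written in the protocol requires new adverse events or vital status after a permanent toxicity withdrawal. On the alternative reading of Section 8 the duty continues, but to an unstated end.

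**The case against.** The strongest reply starts from the rest of the Section 8 sentence, which ties reporting to USF IRB and FDA requirements. Those may reach some later events or deaths. They are not part of the document, so it cannot be said that such events would go unreported. This stands, and it limits the point to the protocol's own rules.

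Nor is being off the drug always an exit. Treatment Duration item D allows Omegaven whenever an eligible infant needs PN and has conjugated bilirubin above 2 mg/dl, and Section 5 allows interruption and resumption. Section 4 also names death and re-hospitalization among toxicities that need assessment and reporting. This too stands: the exit is undefined rather than plainly set at the last infusion. It does not supply an end point for a permanent withdrawal.

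The setting is single-site compassionate use with no power-based sample size, and no safety estimate or test is stated that could be called biased. That is fair. The consequence is an incomplete record, not a demonstrated bias.

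A reader might infer three stronger things that the protocol does not support:

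- **Persisting cholestasis goes unrecorded after withdrawal.** Section 9 sets no cut-off, so this follows only if its collection also stops at withdrawal.
- **Sections 4 and 9 conflict, or the before/after comparison is biased in a known direction.** Section 4 sets a minimum to document and does not forbid later collection. The protocol also does not say how earlier-period data are gathered.
- **The loss can be counted in missed weekly bilirubin panels, using the resolution times in Section 1 (5, 9.4 and 44.1 weeks).** Any such count needs an assumed week of withdrawal. It also needs times from infants on fish oil, or from a historical cohort, to apply to infants who stopped Omegaven. And it would say nothing about adverse events or deaths.

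Section 7's remark on limited evaluation over long treatment concerns prolonged exposure, so it is not evidence about events after an early stop.

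**Conclusion.** The point holds in a limited form. Sections 4 and 8 do not say whether stopping Omegaven ends observation. On a natural reading, the protocol's own rules do not require new adverse events or deaths after a permanent toxicity withdrawal to be recorded, apart from what the IRB and the FDA separately demand. That can understate harm in the safety record.

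This rests on treating a permanent withdrawal as the exit, which the wording favours but does not state. The number of infants affected, and any effect on the before/after comparison, cannot be derived from the protocol. It is a cheap improvement to a stated reporting window, not a flaw that undermines the treatment plan.

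**What to change.** In Section 4, state that stopping Omegaven for any reason does not end observation unless the guardian withdraws from observation. In Section 8, replace the exit with a fixed end point for every infant who received a first infusion, for example a set number of days after the last infusion or hospital discharge, whichever is later. If Omegaven is restarted under item D, count from the most recent infusion. Up to that point, record adverse events, vital status and the Section 9 outcomes from the chart.

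The cost is two or three sentences and some extra chart abstraction for withdrawn infants. No visits or blood draws are added, so laboratory results after stopping will be available only where clinical care produced them. The main downside is interpretive: outcomes after a switch to another emulsion reflect the treatment policy rather than Omegaven alone, and should be labelled so.

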- D. Patient has not responded to other therapeutic approaches for PNALD such as : cycling of PN, avoiding overfeeding, reduction/removal of copper and manganese from PN, advancement of enteral feeding, and use of ursodiol (i.e. Actigal).
- E. Patient has been on at least 2 weeks of SMOFLIPIDs with no improvement or worsening of direct bilirubin levels
- F. Signed patient informed consent
- G. The patient is expected to have a reasonable possibility of survival
- H. No other known etiology of cholestasis other than PNALD at time of Omegaven® initiation

Exclusion Criteria:

- A. Known causes of cholestasis other than PNALD including but not limited to Hepatitis C, Cystic fibrosis, biliary atresia, and alpha 1 anti-trypsin deficiency are present, prior to Omegaven® initiation
- B. Known fish or egg allergy
- C. Any of the contraindications to use of Omegaven®:
 - a) Active new infection at the time of initiation of Omegaven®
 - b) Hemodynamic instability
 - c) Recent use of medications with associated risk of bleeding, including NSAIDs
 - d) Active coagulopathy or bleeding
 - e) Platelet counts persistently under 30,000 despite transfusions
 - f) Unstable hyperglycemia

- g) Impaired lipid metabolism (triglycerides >1000 mg/dL) while on 1 g/kg/day or less of Intralipid
- h) History of severe hemorrhagic disorders (ie. hemophilia, Von Willebrand disease, etc.)
- i) Unstable diabetes mellitus
- j) Collapse and shock
- k) Stroke/ Embolism
- l) Cardiac infarction within the last 3 months
- m) Undefined coma status

In rare instances, patients diagnosed with PNALD may later be found to have liver disease due to other causes in addition to the use of PN (i.e., inborn errors of metabolism, viral infections). These causes may not be known at the time of initiation and will not preclude this patient from continuing Omegaven®.

Baseline labs already collected as standard of care may be used provided it was collected no more than 14 days prior to the start of treatment.

Treatment Duration

- A. This Compassionate Use treatment will end when the results of an FDA approved clinical trial proves Omegaven® treatment to be ineffective or the product is approved for use in the United States.
- B. Patients will remain on Omegaven® until weaned from PN.
- C. In the event that a patient who has been listed for a liver or liver/intestinal transplant has an organ become available, the participation in this protocol will not preclude them from receiving the transplant.

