CBC without Differential (includes WBC, RBC, Hemoglobin, Hematocrit, MCV, MCH, MCHC, RDW, RDW-SD)	X			x
Triglycerides	X			x
Magnesium				x
GGT	X			x

6. Monitoring for Subject/Patient Compliance

The Omegaven® will be administered by trained clinical staff and documented in the Tampa General medical records.

7. Risk/Benefit Assessment

The patient will be at some risk inherent in taking a pharmaceutical agent that has not been fully evaluated for long duration treatment. However, the availability of safety data demonstrates no life-threatening risks or toxicities to vital organs or physiologic functions. Prolonged bleeding times and inhibition of platelet aggregation are a potential risk, especially to those patients with an underlying coagulopathy or those being treated with an anticoagulant. The potential benefits of Omegaven® in this patient population are mainly based on the experimental evidence and a single case of dramatic success. However, the treatment is being used for compassionate care, as no standard therapy is available or appropriate, or has already failed. Omegaven® has been studied in animal pre-clinical models as well as Phase I, II, III, and post marketing human (adults and infants) trials.

Undesirable effects that are seen during the infusion of Omegaven® that may also occur with conventional fat emulsions (i.e., Intralipid®) include:

Uncommon: $\geq 1/1,000, <1/100$:

- Slight rise in body temperature
- Heat sensation and/or cold sensation
- Chills
- Flushing or cyanosis
- Lack of appetite, nausea, vomiting
- Dyspnea
- Headache, pain in the chest, bone pain
- Priapism
- Increase/decrease blood pressure
- Anaphylactic reactions/erythema

Undesirable effects observed during the administration of Omegaven®:

Rare ($\geq 1/10,000$, $<1/1,000$):

- The infusion of Omegaven® can lead to a prolonged bleeding time and an inhibited platelet aggregation
- Fishy taste

Very rare $< 1/10,000$:

- Blood and lymphatic system disorders: very rare: thrombocytopenia, hemolysis, reticulocytosis
- Immune system disorders: very rare: anaphylactic reaction
- Investigations: very rare: transient increase in liver function test
- Reproductive system and breast disorders: very rare: priapism
- Skin and subcutaneous tissue disorders: very rare: rash, urticaria
- Vascular disorders: very rare: circulatory effects (e.g. hyper/hypotension).

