- Thrombocytopenia has been reported in association with prolonged treatment with fat emulsions in infants. Transient increase in liver function tests after prolonged IV nutrition with or without fat emulsions have also been noted.

Other expected adverse events that are common to all patients with chronic intestinal failure, regardless of the type of fat emulsion they receive, include blood stream infections and re-admittance to hospital. Causes for re-hospitalization may include dehydration, bloodstream infections, electrolyte abnormalities, bowel obstruction, and central venous catheter malfunction.

Overdose:

In the event of an overdose of Omegaven®, there is a risk of developing fat overload syndrome that may occur when the triglyceride level rises >300 mg/dL acutely as a result of too rapid a rate of infusion, or chronically at high infusion rates associated with a change in the patient's clinical condition (e.g., renal dysfunction, sepsis). In such cases, the infusion will be stopped or, if necessary, continued at a reduced dose. Metabolic acidosis has occurred in patients receiving Omegaven® at excessive doses without simultaneous administration of dextrose.

Potential Risks of No Treatment

Since Omegaven® will only be offered to those patients for whom no standard therapy is likely to be safe and effective, the risks of not being treated are those allowing for the natural history of their disease and associated clinical manifestations to progress. These include fulminate liver failure and death.

Protection Against Risks

- Treatment safety – Laboratory values will be recorded/monitored as scheduled within Table 1
- We will also monitor growth rate, weight, length, and head circumference growth

Patient Injury

In the case of injury or illness resulting from this study, emergency medical treatment is available. It will be provided at the usual charge.

Potential Benefits to the Patients

- Omegaven® may be effective in stabilizing or reversing hepatic injury associated with the use of parenteral nutrition. It may allow the patient to continue to receive the majority of his/her

caloric intake from parenteral nutrition while advancing on enteral nutrition or awaiting liver or liver/intestinal transplant.

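### Table 1 sets no fixed on-treatment interval for triglycerides, although lipid intolerance (>300 mg/dL) and one withdrawal criterion (>600 mg/dL) are defined by that level alone

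*Protocol*

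**What the plan says.** **Rules that use the level.** Section 5 (Dose Modification / Lipid Intolerance) opens its sequence with lipid intolerance "defined as serum triglyceride levels > 300 mg/dL, the following will be considered prior to reducing the dose". The sequence is a 20-hour infusion with a repeat level, a look for other causes, and then possibly a dose cut of 25% to 50%. Section 4 includes "Triglycerides >600 mg/dL" among the reasons for withdrawal after review by the Principal Investigator. Section 7 (Overdose) also refers to a rise above 300 mg/dL.

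**Schedule that supplies the level.** Section 5 (Primary Safety Outcomes/Endpoints) states: "Lab values will be recorded/monitored as scheduled within Table 1". Section 7 (Protection Against Risks) repeats this. In Table 1 the triglyceride row has two marks: baseline, no more than 14 days before treatment, and the column headed "Periodically as clinically indicated". The weekly and 4-weekly cells are empty. The hepatic function panel is marked at baseline and weekly.

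**Who enters.** Inclusion criterion E reads "Patient has been on at least 2 weeks of SMOFLIPIDs", without improvement in direct bilirubin. The only triglyceride exclusion, criterion C(g) in Section 3, is a level above 1000 mg/dL on 1 g/kg/day or less of Intralipid.

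**The concern.** A threshold defined by a blood level works only if the blood level is taken. Here both definitions rest on the number alone, with no accompanying sign to alert staff, while the on-treatment measurement is left to clinical indication and the indication is not stated. An infant whose triglycerides rise without outward signs may therefore not be tested, and the Section 5 steps and the Section 4 review would not be prompted.

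There is also a reporting consequence. Table 1 laboratory values are the first item under the primary safety outcomes. If triglycerides are drawn mainly when someone is worried, the recorded values come from a selected group of infants and times. An infant with no recorded level cannot be counted as normal.

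**Working it through.** The protocol gives no figure to reproduce. The check sets the rules beside the schedule.

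**1. Count the marks.** Triglyceride row of Table 1: baseline 1, weekly 0, 4-weekly 0, periodic 1. So there is an on-treatment mark, but no fixed interval.

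**2. Is the column reading safe?** The hepatic row (baseline and weekly) and the magnesium row (periodic only) fit the same four columns, so a shift in the extracted text is unlikely. A blank cell alone proves little, however. Weight is marked only at baseline, yet Section 5 requires it three times a week. The difference is that the text supplies the interval for weight, and no section supplies one for triglycerides. The weekly heading carries an asterisk whose footnote is not in the extracted text; nothing here relies on it.

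**3. Other on-treatment levels in the text.** Section 5 requires a repeat level after the change to a 20-hour infusion, and its dose-cut step presupposes that levels are still being followed. Both come after a first high level and do not schedule that first level.

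**4. What would prompt the first level?** For other discretionary tests Section 5 names a prompt: suspicion of a bleeding disorder for the coagulation panel, and clinical suspicion or prolonged use below 1 g/kg/day for essential fatty acid testing. It names none for triglycerides. Section 8 has adverse events detected in standard care, "including the routine monitoring of vital signs and daily physical exam data". Neither example measures triglycerides, though the list is not exhaustive.

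**5. Does the baseline level cover the gap?** It precedes Omegaven, may be 14 days old, and comes from infants who have had at least 2 weeks of another emulsion. It does not show tolerance of Omegaven. Set beside the action levels:

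| Baseline triglycerides (mg/dL) | Excluded by C(g)? | Position against the on-treatment thresholds |
|---|---|---|
| up to 300 | no | below both |
| above 300, up to 600 | no | above the Section 5 level |
| above 600, up to 1000 | no | above the Section 5 and Section 4 levels |
| above 1000 on 1 g/kg/day or less of Intralipid | yes | not enrolled |

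An infant in the second or third row may start treatment already above an action level, with no fixed recheck.

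**6. What do the cited data say about frequency?** Section 1 reports no hypertriglyceridemia in a fish-oil cohort of 18 infants. If all 18 were assessed, the one-sided 95% upper bound for the rate is 1 − 0.05^(1/18) = 0.153, about 15%. The cut-off used in that cohort is not given. The finding is reassuring but does not exclude a rate that would matter. A second cohort, of 79 infants, showed improved triglycerides on average, which does not give the share above 300 mg/dL.

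**The case against.** The strongest reply is that the protocol does provide for on-treatment levels. The periodic column is an on-treatment column, and Section 5 (Omegaven Administration) says that the same standards of care apply as for all infants on PN and that hospital policy for lipid emulsions governs dispensing. Those standards may include routine triglycerides. This stands, and it limits the point. A reader might infer that the protocol calls for no triglyceride level on Omegaven, or that the dose and withdrawal rules can never come into play. The documents do not support that: it would give the periodic mark no meaning and would assume the content of a local standard that is not shown.

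Second, the actions are discretionary. The Section 5 steps are to be considered, and Section 4 lists possible reasons subject to review. That is so, but discretion over the response still needs a value to respond to.

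Third, the cited cohorts are reassuring, the dose is 1 g/kg/day with a rate cap, and testing on indication is a defensible choice in small infants. This argues for a modest grading. It does not explain why a sign-free threshold has neither an interval nor a stated prompt.

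Fourth, this is compassionate use with no power basis, and estimating the frequency of lipid intolerance is not a stated aim. That stands too. The reporting consequence concerns description of a listed safety outcome, not a test.

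**Conclusion.** The point holds in a limited form. Triglycerides have no fixed on-treatment interval in Table 1 or elsewhere in the protocol, while lipid intolerance in Section 5 and one withdrawal criterion in Section 4 are defined by the level with no clinical sign. Infants with baseline levels above 300 and up to 1000 mg/dL are not excluded on that ground. Unless local PN care supplies routine levels, an infant without signs could exceed 300 or 600 mg/dL undetected, and the recorded values would be a selected sample.

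The number of infants affected cannot be derived, because the protocol gives neither the share passing 300 mg/dL without signs nor the local testing practice. A reader might take the total emulsion infused between levels as a measure of the risk. It is only dose multiplied by days and says nothing about how often triglycerides rise.

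The conclusion assumes that the extracted column order is right, which the hepatic and magnesium rows support, and that no lost footnote sets a triglyceride interval. It is a change worth making for safety monitoring and for the completeness of a listed safety outcome; it is not evidence of harm.

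**What to change.** In Table 1, mark triglycerides in the weekly column, drawn with the weekly hepatic panel:

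- First level within 7 days of starting Omegaven.
- One level within 7 days after any change of dose or infusion hours.
- Step down to the existing 4-weekly column after four weekly levels of 300 mg/dL or less.
- Keep the as-indicated mark for extra levels.

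**Cost.** One analyte is added to a draw that is already scheduled, with no extra visit. For a 3-week course (the minimum expected PN need in inclusion criterion C) this is 3 levels. For an 18-week course (the median time on fish oil in one cited cohort) with step-down it is weeks 1 to 4 plus weeks 8, 12 and 16, so 4 + 3 = 7 levels, against 18 if weekly throughout. Levels after a change of dose or infusion hours may add to this once the infant is on the 4-weekly schedule. The downside is a small added blood volume per draw, which matters in small infants and is not quantified in the protocol; the step-down limits it. If local PN care already includes routine triglycerides, the edit only writes existing practice into Table 1.
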